XXXXXXXXXX/ XXXX-XXXX	Cycle 4	Yes/No	ddmmYYYY/ xx	Normal		
	Visit 8	Yes/No	ddmmYYYY/ xx	Clinically insignificant abnormality		
		Yes/No	ddmmYYYY/ xx	Clinically significant abnormality	XXXXXXXXXXXXXXXXXXXX XXXXXXXXXXXXXXXXXXXX XXXXXXXXXXXXXXXXXXXX XXXXXXXXXXXXXXXXXXXX	New or worsened Not compared Unchanged

Day is calculated relative to the day of first dose of study medication.

Programming note: Data ordered by country (alphabetically) then centre/patient identifier and visit date. Multiple clinically significant abnormality details should be listed in the order they appear on the CRF.

Listing 16.2-7.2 (page 1 of n)
Imaging
All Patients

Country/ Centre/ Patient	Visit	Date of Scan/Day	Scan Category	Location/ Site	Scan Type	Findings
XXXXXXXXXX/ XXXX-XXXX	Screening Visit 1a	ddmmYYYY/ xx	Chest, Abdomen and Pelvis	Other: xxxxxxxx	CT scan (with contrasts)	xxxxxxx
		ddmmYYYY/ xx	Brain	Other: xxxxxxxx	CT scan (with contrasts)	xxxxxxx
		ddmmYYYY/ xx	Bone	Bone		xxxxxxx
...						

Day is calculated relative to the day of first dose of study medication.

Programming note: Data ordered by country (alphabetically) then centre/patient identifier and visit date.

Listing 16.3-1.1 (page 1 of n)
 Hematology by Visit
 All Treated Patients

Country/ Centre/ Patient	Visit	Sample Date/ Day	Laboratory Number / Name	Parameter	Result (units)	CTC Grade
XXXXXXXXXX/ XXXX-XXXX	Screening Visit 1a	ddmmYYYY/ xx	XXXXXXXXXXXX/ XXXXXX	WBC	xx (unit)	Xx
				Hemoglobin	xx (unit)	Xx
				Platelets	xx (unit)	Xx
				Hematocrit	xx (unit)	
				Neutrophils	xx (unit)	Xx
				Lymphocytes	xx (unit) L	
				Eosinophils	xx (unit)	
				Basophils	xx (unit)	
				Monocytes	xx (unit) H	
				Other: xxxxx	xx (unit)	
	Baseline Visit 1b	ddmmYYYY/ xx	XXXXXXXXXXXX/ XXXXXX	WBC	xx (unit)	Xx
				Hemoglobin	xx (unit)	Xx

L=Low and H=High relative to normal ranges.
 Day is calculated relative to the day of first dose of study medication.

Programming note: Data ordered by country (alphabetically) then centre/patient identifier then by visit date. Any unscheduled assessments should be included and labeled "Unscheduled Visit".

Listing 16.3-2.1 (page 1 of n)
 Blood Chemistry by Visit
 All Treated Patients

Country/ Centre/ Patient	Visit	Sample Date/ Day	Laboratory Number / Name	Parameter	Result (units)	CTC Grade
XXXXXXXXXX/ XXXX-XXXX	Screening Visit 1a	ddmmmyyyy/ xx	XXXXXXXXXX/ XXXXXXXXXX	Urea	xx (unit)	
				BUN	xx (unit)	
				Creatinine	xx (unit) L	Xx
				LDH	xx (unit) L	
				Total Protein	xx (unit) L	
				Albumin	xx (unit)	Xx
				Total Bilirubin	xx (unit)	Xx
				SGOT (AST)	xx (unit)	Xx
				SGPT (ALT)	xx (unit)	Xx
				Alkaline Phosphatase	xx (unit)	Xx
	Baseline Visit 1b	ddmmmyyyy/ xx	XXXXXXXXXX/ XXXXXXXXXX	Urea	xx (unit)	
BUN				xx (unit)		

L=Low and H=High relative to normal ranges.
 Day is calculated relative to the day of first dose of study medication.

Programming note: Data ordered by country (alphabetically) then centre/patient identifier then by visit date. Any unscheduled assessments should be included and labeled "Unscheduled Visit".

Listing 16.3-3.1 (page 1 of n)
 Serum Lipid Profile by Visit
 All Treated Patients

Country/ Centre/ Patient	Visit	Sample Date/ Day	Laboratory Number / Name	Parameter	Result (units)	CTC Grade
XXXXXXXXXX/ XXXX-XXXX	Screening Visit 1a	ddmmmyyyy/ xx	XXXXXXXXXX/ XXXXXXXXXX	Total	xx (unit)	Xx
				Cholesterol		
				Triglycerides	xx (unit)	Xx
				LDL	xx (unit) L	
				HDL	xx (unit) L	
	Baseline Visit 1b	ddmmmyyyy/ xx	XXXXXXXXXX/ XXXXXXXXXX	Total	xx (unit)	xx
Cholesterol						
				Triglycerides	xx (unit)	xx

L=Low and H=High relative to normal ranges.
 Day is calculated relative to the day of first dose of study medication.

Programming note: Data ordered by country (alphabetically) then centre/patient identifier then by visit date. Any unscheduled assessments should be included and labeled "Unscheduled Visit".

Listing 16.3-4.1 (page 1 of n)
 Coagulation by Visit
 All Treated Patients

Country/ Centre/ Patient	Visit	Sample Date/ Day	Laboratory Number / Name	Parameter	Result (units)
XXXXXXXXXX/ XXXX-XXXX	Screening Visit 1a	ddmmyyyy/ xx	XXXXXXXXXX/ XXXXXXXXXX	PT	xx (unit)
				INR	xx (unit) L
	Cycle 2 Visit 4	ddmmyyyy/ xx	XXXXXXXXXX/ XXXXXXXXXX	PT	xx (unit) L
				INR	xx

L=Low and H=High relative to normal ranges.
 Day is calculated relative to the day of first dose of study medication.

Programming note: Data ordered by country (alphabetically) then centre/patient identifier then by visit date. Any unscheduled assessments should be included and labeled "Unscheduled Visit".

Listing 16.3-5.1 (page 1 of n)
 Urinalysis Dipstick Analysis by Visit
 All Treated Patients

Country/ Centre/ Patient	Visit	Sample Date/ Day	Laboratory Number / Name	Parameter	Result
XXXXXXXXXX/ XXXX-XXXX	Screening Visit 1a	ddmmyyyy/ xx	XXXXXXXXXX/ XXXXXXXXXX	Specific Gravity	Xx
				pH	Xx L
				Protein	Xx
				Glucose	Xx
				Bilirubin	Xx
				Ketones	Xx
				Blood Cells	Xx
				Leukocytes	Xx
XXXXXXXXXX/ XXXX-XXXX	Screening Visit 1a	ddmmyyyy/ xx	XXXXXXXXXX/ XXXXXXXXXX	Specific Gravity	Xx L
				pH	Xx
				Protein	Xx
				Glucose	Xx
				Bilirubin	Xx
				Ketones	Xx
				Blood Cells	Xx
				Leukocytes	Xx

L=Low and H=High relative to normal ranges.
 Day is calculated relative to the day of first dose of study medication.

Programming note: Data ordered by country (alphabetically) then centre/patient identifier then by visit date. Any unscheduled assessments should be included and labeled "Unscheduled Visit".

Novartis
IMP : Everolimus
Protocol No.: CRAD001LIC01

Confidential

Date : 22SEP2017
Version : 2
Status : Final
Page : 92 of 101

Listing 16.3-5.2 (page 1 of n)
Urinalysis Microscopic Analysis by Visit
All Treated Patients

Country/ Centre/ Patient	Visit	Sample Date/ Day	Any Abnormal Results	Sample Name	Result	Value
XXXXXXXXXX/ XXXX-XXXX	Screening Visit 1a	ddmmYYYY/ xx	No			
XXXXXXXXXX/ XXXX-XXXX	Screening Visit 1a	ddmmYYYY/ xx	No			
XXXXXXXXXX/ XXXX-XXXX	Screening Visit 1a	ddmmYYYY/ xx	Yes	UWBC/HPF Present Casts/LPF Present	Not Present Present	 xxxx

Day is calculated relative to the day of first dose of study medication.

Programming note: Data ordered by country (alphabetically) then centre/patient identifier then by visit date. Any abnormal results will be sorted by the order they appear on the CRF.

Listing 16.4-1.1 (page 1 of n)
 Concomitant Medications and Non-Drug Therapies
 All Treated Patients

Country/ Centre/ Patient	ATC Class/ Preferred Term/ Medication or Non-Drug Therapy	Dose	Frequency	Route	Reason	Start Date/ Day	End Date/ Day
XXXXXXXXXX/ XXXX-XXXX	XXXXXXXXXX/ XXXXXXXXXXXXXXXXXX ^	Xx mg	2x daily	PO	XXXXXXXXXXXX	ddmmyyyy/ xx	ddmmyyyy/ xx
	XXXXXXXXXX/ XXXXXXXXXXXXXXXXXX	Xx mg	XXXXXX	Nasal	XXXXXXXXXXXX	ddmmyyyy/ xx	ddmmyyyy/ xx
	XXXXXXXXXX/ XXXXXXXXXXXXXXXXXX	Xx	On demand	Other	XXXXXXXXXXXX	ddmmyyyy/ xx	ddmmyyyy/ xx
	XXXXXXXXXX/ XXXXXXXXXXXXXXXXXX	Xx mg	1x weekly	Oral	XXXXXXXXXXXX	ddmmyyyy/ xx	Ongoing
	XXXXXXXXXX/ XXXXXXXXXXXXXXXXXX	Xx mg	2x daily	PO	XXXXXXXXXXXX	ddmmyyyy/ xx	Ongoing
XXXXXXXXXX/ XXXX-XXXX	XXXXXXXXXX/ XXXXXXXXXXXXXXXXXX ^	Xx mg	XXXXXX	Nasal	XXXXXXXXXXXX	ddmmyyyy/ xx	ddmmyyyy/ xx
	XXXXXXXXXX/ XXXXXXXXXXXXXXXXXX	Xx mg	XXXXXX	Nasal	XXXXXXXXXXXX	ddmmyyyy/ xx	ddmmyyyy/ xx

Day is calculated relative to the day of first dose of study medication.

^ Prior Medication

Programming note: Data ordered by country (alphabetically) then centre/patient identifier then by medications/therapies in order of start date (oldest first). Where unit or frequency have been recorded as "other" and then specified, it is only necessary to show the text in the specification (rather than Other: xxxxx). For route it appears from the CRF design that there is no further specification if "Other" is recorded so in this case the listing should just present "Other".

Listing 16.4-2.1 (page 1 of n)
Antineoplastic Therapy Since Discontinuation of Study Drug
All Treated Patients

Country/ Centre/ Patient	Regimen Number	Therapy Type	Medication/ Non-Drug Therapy	Start Date/ Day	Stop Date/ Day
XXXXXXXXXX/ XXXX-XXXX	1	Chemotherapy	XXXXXXXXXX	ddmmmyyyy/ xx	Ongoing
XXXXXXXXXX/ XXXX-XXXX	1	Immunotherapy	XXXXXXXXXX	ddmmmyyyy/ xx	ddmmmyyyy/ xx
XXXXXXXXXX/ XXXX-XXXX	1	Other: XXXXXXXXXX	XXXXXXXXXX	ddmmmyyyy/ xx	ddmmmyyyy/ xx

Day is calculated relative to the day of first dose of study medication.

Programming note: Data ordered by country (alphabetically) then centre/patient identifier. Therapy should be ordered by Regimen Number.

Listing 16.5-1.1 (page 1 of n)
 All Adverse Events
 All Treated Patients

Country/ Centre/ Patient	System Organ Class/ Preferred Term/ Verbatim	Serious Adverse Event	Grade	Relationship Suspected? / Action Taken	Resulted in Death?	Start Date/ Day	End Date/ Day	Treatment Emergent Event
XXXXXXXXXX/ XXXX-XXXX	XXXXXXXXXX/ XXXXXXXXXXXXXXXXXX/ XXXXXXXXXX	Yes	4	No/ No Action Taken	No	ddmmmyyyy/ xx	ddmmmyyyy/ xx	No
	XXXXXXXXXX/ XXXXXXXXXXXXXXXXXX/ XXXXXXXXXXXXXXXXXX	No	2	No/ Conmed Given	No	ddmmmyyyy/ xx	ddmmmyyyy/ xx	Yes
	XXXXXXXXXX/ XXXXXXXXXXXXXXXXXX/ XXXXXXXXXXXXXXXXXX	No	1	Yes/ Temporarily stopped study drug	No	ddmmmyyyy/ xx	ddmmmyyyy/ xx	Yes
	XXXXXXXXXX/ XXXXXXXXXXXXXXXXXX/ XXXXXXXXXXXXXXXXXX	No	1	No/ No action taken	No	ddmmmyyyy/ xx	Ongoing	Yes
XXXXXXXXXX/ XXXX-XXXX	XXXXXXXXXX/ XXXXXXXXXXXXXXXXXX/ XXXXXX	No	2	No/ Permanently stopped study drug	Yes	ddmmmyyyy/ xx	ddmmmyyyy/ xx	No

Day is calculated relative to the day of first dose of study medication.
 Adverse events are flagged as resulting in death if the patient dies and the AE end date is the day of death or is missing.

Programming note: Data ordered by country (alphabetically) then centre/patient identifier then by adverse event in order of start date (oldestfirst).

The following listings will follow this format:
 Listing 16.5-2.1 Deaths Reportable as SAEs - All Patients
 Listing 16.5-2.2 Non-Fatal SAEs - All Patients

Listing 16.6-1.1 (page 1 of n)
 RECIST Solid Tumor Response Assessment - Target Lesions
 All Treated Patients

Country/ Centre/ Patient	Visit	Visit Date/ Day	Lesion Number	Location	Evaluation Method	Date of Baseline Evaluation	Baseline Evaluation Method	Date of Evaluation 1	Evaluation 1 (mm)	
XXXXXXXXXX/ XXXX-XXXX	Cycle 3 Visit 7	ddmmYYYY/ xx	1	XXXXXXXX	4	ddmmYYYY	4	ddmmYYYY	xx.x	
	Cycle 6 Visit 10	ddmmYYYY/ xx	1	XXXXXXXX	4	ddmmYYYY	4	ddmmYYYY	xx.x	
	Cycle 9 Visit 13	ddmmYYYY/ xx	2	XXXXXXXX	4	ddmmYYYY	4	ddmmYYYY	xx.x	
	Cycle 12 Visit 16	ddmmYYYY/ xx	1	XXXXXXXX	4	ddmmYYYY	4	ddmmYYYY	xx.x	
	Cycle 15 Visit 19	ddmmYYYY/ xx	2	XXXXXXXX	4	ddmmYYYY	4	ddmmYYYY	xx.x	
				1	XXXXXXXX	4	ddmmYYYY	4	ddmmYYYY	xx.x
				2	XXXXXXXX	4	ddmmYYYY	4	ddmmYYYY	xx.x
				2	XXXXXXXX	4	ddmmYYYY	4	ddmmYYYY	xx.x

Day is calculated relative to the day of first dose of study medication.

Programming note: Data ordered by country (alphabetically) then centre/patient identifier then visit. Lesions should be sorted by Lesion Number. Any unscheduled assessments should be included and labeled "Unscheduled Visit".

Listing 16.6-1.2 (page 1 of n)
 RECIST Solid Tumor Response Assessment - Non-Target Lesions
 All Treated Patients

Country/ Centre/ Patient	Visit	Visit Date/ Day	Lesion Number	Location	Evaluation Method	Date of Baseline Evaluation	Baseline Evaluation Method	Date of Evaluation 1	Evaluation 1	
XXXXXXXXXX/ Xxxx-xxxxx	Cycle 3 Visit 7	ddmmYYYY/ xx	1	XXXXXXXX	4	ddmmYYYY	4	4	XXXXXXXX	
	Cycle 6 Visit 10	ddmmYYYY/ xx	1	XXXXXXXX	4	ddmmYYYY	4	4	XXXXXXXX XXXXXXXX	
	Cycle 9 Visit 13	ddmmYYYY/ xx	2 1	XXXXXXXX XXXXXXXX	4 4	ddmmYYYY ddmmYYYY	4 4	4 4	XXXXXXXX XXXXXXXX	
	Cycle 12 Visit 16	ddmmYYYY/ xx	2 1	XXXXXXXX XXXXXXXX	4 4	ddmmYYYY ddmmYYYY	4 4	4 4	XXXXXXXX XXXXXXXX	
	Cycle 15 Visit 19	ddmmYYYY/ xx	2 1	XXXXXXXX XXXXXXXX	4 4	ddmmYYYY ddmmYYYY	4 4	4 4	XXXXXXXX XXXXXXXX	
				2	XXXXXXXX	4	ddmmYYYY	4	4	XXXXXXXX

Day is calculated relative to the day of first dose of study medication.

Programming note: Data ordered by country (alphabetically) then centre/patient identifier then visit. Lesions should be sorted by Lesion Number. Any unscheduled assessments should be included and labeled "Unscheduled Visit".

Listing 16.6-1.3 (page 1 of n)
 RECIST Solid Tumor Response Assessment - Overall Response
 All Treated Patients

Country/ Centre/ Patient	Visit	Visit Date/ Day	Evaluation Number	Date of Response	Overall Lesion Response
XXXXXXXXXX/ XXXX-XXXX	Cycle 3 Visit 7	ddmmYYYY/ xx	1	ddmmYYYY	XXXXXXXX
	Cycle 6 Visit 10	ddmmYYYY/ xx	2 1	ddmmYYYY ddmmYYYY	XXXXXXXX XXXXXXXX
	Cycle 9 Visit 13	ddmmYYYY/ xx	2 1	ddmmYYYY ddmmYYYY	XXXXXXXX XXXXXXXX
	Cycle 12 Visit 16	ddmmYYYY/ xx	2 1	ddmmYYYY ddmmYYYY	XXXXXXXX XXXXXXXX
	Cycle 15 Visit 19	ddmmYYYY/ xx	2 1	ddmmYYYY ddmmYYYY	XXXXXXXX XXXXXXXX
			2	ddmmYYYY	XXXXXXXX

Day is calculated relative to the day of first dose of study medication.

Programming note: Data ordered by country (alphabetically) then centre/patient identifier then visit. Evaluations should be sorted by Evaluation Number. Any unscheduled assessments should be included and labeled "Unscheduled Visit".

Listing 16.6-1.4 (page 1 of n)
 Survival Status at End of Study
 All Treated Patients

Country/ Centre/ Patient	Current Status	Death Date/ Day	Principal Cause of Death	Last Contact Date/ Day
XXXXXXXXXX/ XXX-XXXX	Alive			ddmmyyyy/ xx
XXXXXXXXXX/ XXX-XXXX	Lost to Follow-up			ddmmyyyy/ xx
XXXXXXXXXX/ XXX-XXXX	Dead	ddmmyyyy/ xx	Other: xxxxxxxxxxxxxxxxxxxxxxxxx	
XXXXXXXXXX/ XXX-XXXX	Alive			ddmmyyyy/ xx
XXXXXXXXXX/ XXX-XXXX	Dead	ddmmyyyy/ xx	Study Indication	

Day is calculated relative to the day of first dose of study medication.

Programming note: Data ordered by country (alphabetically) then centre/patient identifier.

Novartis
 IMP : Everolimus
 Protocol No.: CRAD001LIC01

Confidential

Date : 22SEP2017
 Version : 2
 Status : Final
 Page : 100 of 101

Listing 16.6-1.5 (page 1 of n)
 Progression and Survival Details
 All Treated Patients

Country/ Centre/ Patient	Progression Status	Date of First Progression Event	Days from Start of Treatment to Progression	Survival Status	Date of Death/ Last Contact	Days from Start of Treatment to Death	Disease Control	Objectiv e Response	Duration of Response (Days)
XXXXXXXXXX/ XXXX-XXXX	Progression	ddmmmyyy	xx	Dead	ddmmmyyy	xx	No	No	
XXXXXXXXXX/ XXXX-XXXX	No Progression	ddmmmyyy	xx^	Alive	ddmmmyyy	xx^	Yes	Yes	xx
XXXXXXXXXX/ XXXX-XXXX	Progression	ddmmmyyy	xx	Alive	ddmmmyyy	xx^	No	No	
XXXXXXXXXX/ XXXX-XXXX	No Progression	ddmmmyyy	xx^	Alive	ddmmmyyy	xx^	Yes	Yes	xx^

^Censored

Programming note: Data ordered by country (alphabetically) then centre/patient identifier.

Novartis
IMP : Everolimus
Protocol No.: CRAD001LIC01

Confidential

Date : 22SEP2017
Version : 2
Status : Final
Page : 101 of 101

Listing 16.7-1.1 (page 1 of n)
Comments Listing
All Patients

Country/ Centre/ Patient	Cycle	Page Number	Comments
XXXXXXXXXX/ XXXX-XXXX	Cycle 1	Xxx	XXXXXXXX XXXXXX XXXX XXXXXXXXXXXX XXXXXX XXXXXXXXXXXXXXXXXXXX XXXXXXXXXXXXXXXXXXXX
	Cycle 4	Xxx	XXXXXXXX XXXXXX XXXX XXXXXXXXXXXX XXXXXX
XXXXXXXXXX/ XXXX-XXXX XXXXXXXXXX/ XXXX-XXXX	Cycle 2	Xxx	XXXXXXXX XXXXXX XXXX XXXXXXXXXXXX XXXXXX
	End of Treatment	Xx	XXXXXXXX XXXXXX XXXX XXXXXXXXXXXX XXXXXX

Programming note: Data ordered by country (alphabetically) then centre/patient identifier then by cycle and page number.

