10.4.2 Statistical Hypothesis, Model, and Method of Analysis

No statistical test of hypotheses will be performed in this study.

The primary analysis for this study is to estimate the PFS rate over time and its 95% CI by the method of Kaplan-Meier for:

1. All patients;
2. First-line patients (receiving RAD001 as their first treatment);
3. Second-line patients (patients who received cytokine therapy as first-line therapy).

Progression-free survival curves (graphing the PFS rate over time) will be displayed, overall and by strata, according to the Kaplan-Meier product-limit method. The PFS rate over time will also be tabulated. The resulting median PFS time will be given with 95% CIs.

The primary analysis will be performed on the Full Analysis Set (FAS). Consolidated summary results obtained from the local radiological review will be used for this analysis.

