7.2 Data handling

7.2.1 Calculation of time-to-event

In the following definitions the time of study entry has been defined as date of first dose of study medication (taken from the dosage administration record on the CRF).

The date of last contact (used in the censoring rules below) is collected on the End of Study/Survival Information page of the CRF. However, it should be noted that it is only planned for contact with patients to take place at the clinic visits and so the date of last contact captured on the CRF should always be equal to the date of last visit attended.

Progression Free Survival:

PFS is defined as the time from date of first dose of study medication until the date of the first documented disease progression or death due to any cause. Date of progression and date of death will be captured on the CRF.

For the purpose of calculating the PFS Rate if a patient has not progressed or died at the date of analysis cut-off, or when he/she received further anticancer therapy, then their time to progression or death will be censored at the time of last tumor assessment, before the first cut-off date or the anticancer therapy date.

Progression Free Survival Rate:

The PFS rate is defined as the survival function at the end of the time point based on a Kaplan-Meier analysis of the time to either progression (as per the local radiological review) or death (see next section for handling of censored data).

The time points at which PFS rate will be summarized are: 8 weeks, 20 weeks, 32 weeks, 44 weeks, 56 weeks and every 12 weeks thereafter as appropriate.

Overall Survival:

Overall survival is defined as the time from date of first dose of study medication until death due to any cause. The date of death will be captured on the CRF.

If a patient is still alive and not lost to follow-up at the end of the study then their time to death will be censored at the date of last contact date, as recorded on the CRF.

If the patient has been lost to follow-up by the end of the study then their time to death will be censored at the date of last contact as recorded on the CRF.

In the event that a date of last contact has not been recorded on the CRF, then the date of the last assessment recorded should be used instead.

Duration of Response:

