7.6 Time to Event Analysis

At each visit where tumor assessment is performed the CRF will capture the RECIST assessment of tumor response according to local radiological review. If disease progression occurs then the End of Treatment pages of the CRF should be completed.

The patient's status at the end of study will be summarized with patients being classed as either alive, dead or lost to follow-up and either having had a relapse/recurrence or not. Further, if the patient has died it will be summarized whether death was due to study indication or not. These summaries will be performed on the ITT population.

The time to event variables are defined in Section 7.2.1.

No statistical test of hypotheses will be performed in this study. PFS rate and 95% confidence intervals will be presented graphically and tabulated, overall and by strata, using the Kaplan-Meier product-limit method. The resulting median PFS will be presented along with 95% CIs. These analyses will be performed on the ITT population.

The analysis of PFS will be repeated for the sensitivity analyses described in Section 7.2.3 and also for Duration of Response.

For Overall Survival the Kaplan-Meier curve will be displayed and the median, 25th and 75th percentile of the Kaplan-Meier estimate will be reported for the ITT population.

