	No recurrence	xx (xx.x%)
Lost to follow-up	Overall	xx (xx.x%)
	Already experienced recurrence	xx (xx.x%)
	No recurrence	xx (xx.x%)

Percentages are based on the number of patients in ITT population.
 With recurrence refers to subjects that had disease progression prior to death.
 Source: Listings 16.6-1.2 and 16.6-1.4

Table 14.6-2.1 (page 1 of 1)
Analysis of Progression Free Survival Rate
Population ITT

	First-line Patients N = xxxx	Second-line Patients N = xxxx	Total N = xxxx
PFS Events	xxx	xxx	xxx
PFS Rate	xx.xx	xx.xx	xx.xx
95% CI for PFS Rate	(xx.xxx, xx.xxx)	(xx.xxx, xx.xxx)	(xx.xxx, xx.xxx)

Number of patients achieving PFS = number of subject that experienced progression or died prior to the time of data analysis cut-off.

PFS Rate = survival function at the time of data analysis cut-off based on a Kaplan-Meier analysis of time to either progression or death.

The 95% CI also comes from the Kaplan-Meier analysis.

Source: Listings 16.6-1.5

Table 14.6-2.2 (page 1 of 1)
 Analysis of Progression Free Survival Rate - Sensitivity Analysis
 Population ITT

	First-line Patients N = xxxx	Second-line Patients N = xxxx	Total N = xxxx
Sensitivity Analysis 1:			
PFS Events	xxx	xxx	xxx
PFS Rate	xx.xx	xx.xx	xx.xx
95% CI for PFS Rate	(xx.xxx, xx.xxx)	(xx.xxx, xx.xxx)	(xx.xxx, xx.xxx)
Sensitivity Analysis 2:			
PFS Events	xxx	xxx	xxx
PFS Rate	xx.xx	xx.xx	xx.xx
95% CI for PFS Rate	(xx.xxx, xx.xxx)	(xx.xxx, xx.xxx)	(xx.xxx, xx.xxx)

Number of patients achieving PFS = number of subject that experienced progression or died prior to the time of data analysis cut-off.

PFS Rate = survival function at the time of data analysis cut-off based on a Kaplan-Meier analysis of time to either progression or death.

The 95% CI also comes from the Kaplan-Meier analysis.

Sensitivity Analysis 1 = Actual event date of disease progression/death used for the PFS event date, regardless of whether is it proceeded by missing tumor assessments.

Sensitivity Analysis 2 = In case of a documented progression/death after one of more missing tumor assessments, disease progression is considered to have occurred at the next scheduled tumor assessment after the date of last tumor assessment with overall lesion response of CR, PR, or SD.

Source: Listings 16.6-1.5

Table 14.6-2.3 (page 1 of 2)
 Progression Free Survival Descriptive Statistics
 Population ITT

Time to Event	Censored *	Event #	Product Limit Estimates			
			Survival Rate	95% CI of Survival Rate	Failure Rate	Survival Standard Error

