<= Week 8	xx	xx	x.xxxx	(x.xxxx-x.xxxx)	x.xxxx	x.xxxx
<=Week 20	xx	xx	x.xxxx	(x.xxxx-x.xxxx)	x.xxxx	x.xxxx
<=Week 32	xx	xx	x.xxxx	(x.xxxx-x.xxxx)	x.xxxx	x.xxxx
<=Week 44	xx	xx	x.xxxx	(x.xxxx-x.xxxx)	x.xxxx	x.xxxx
<=Week 56	xx	xx	x.xxxx	(x.xxxx-x.xxxx)	x.xxxx	x.xxxx
Etc.						

* Censored is defined as the number of patients who have discontinued from the study for any reason other than progression/death within the time period.

Event is progression/death within the time period.

Source: Listings 16.6-1.5

Programming Note: Table continues for every 12 week assessment as appropriate until analysis data cut-off.

Table 14.6-2.3 (page 2 of 2)
Progression Free Survival Descriptive Statistics
Population ITT

	Total
	N = xxxx

Median (95% CI)	xx.xx (xx.xxx)
Number Assessed	xx
Number Censored	xx
Number Uncensored	xx

Source: Listings 16.6-1.5

Programming Note: Use previous template for the following tables.

- Table 14.6-2.5 Duration of Response Descriptive Statistics - Population ITT

Novartis
 IMP : Everolimus
 Protocol No.: CRAD001LIC01

Confidential

Date : 22SEP2017
 Version : 2
 Status : Final
 Page : 59 of 101

Table 14.6-2.4 (page 1 of 4)
 Progression Free Survival Descriptive Statistics - Sensitivity Analysis
 Population ITT

Time to Event	Censored *	Event #	Product Limit Estimates			
			Survival Rate	95% CI of Survival Rate	Failure Rate	Survival Standard Error
Sensitivity Analysis 1:						
<= Week 8	xx	xx	x.xxxx	(x.xxxx-x.xxxx)	x.xxxx	x.xxxx
<=Week 20	xx	xx	x.xxxx	(x.xxxx-x.xxxx)	x.xxxx	x.xxxx
<=Week 32	xx	xx	x.xxxx	(x.xxxx-x.xxxx)	x.xxxx	x.xxxx
<=Week 44	xx	xx	x.xxxx	(x.xxxx-x.xxxx)	x.xxxx	x.xxxx
<=Week 56	xx	xx	x.xxxx	(x.xxxx-x.xxxx)	x.xxxx	x.xxxx
Etc.						

* Censored is defined as the number of patients who have discontinued from the study for any reason other than progression/death within the time period.

Event is progression/death within the time period.

Sensitivity Analysis 1 = Actual event date of disease progression/death used for the PFS event date, regardless of whether is it proceeded by missing tumor assessments.

Sensitivity Analysis 2 = In case of a documented progression/death after one of more missing tumor assessments, disease progression is considered to have occurred at the next scheduled tumor assessment after the date of last tumor assessment with overall lesion response of CR, PR, or SD.

Source: Listings 16.6-1.5

Programming Note: Table continues for every 12 week assessment as appropriate until analysis data cut-off.

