Table 14.6-2.4 (page 2 of 4)
Progression Free Survival Descriptive Statistics - Sensitivity Analysis
Population ITT

	Total
	N = xxxx

Sensitivity 1:

Median (95% CI)	xx.xx (xx.xxx)
Number Assessed	xx
Number Censored	xx
Number Uncensored	xx

Sensitivity Analysis 1 = Actual event date of disease progression/death used for the PFS event date, regardless of whether is it proceeded by missing tumor assessments.
Sensitivity Analysis 2 = In case of a documented progression/death after one of more missing tumor assessments, disease progression is considered to have occurred at the next scheduled tumor assessment after the date of last tumor assessment with overall lesion response of CR, PR, or SD.

Source: Listings 16.6-1.5

Programming Note: Repeat for Sensitivity Analysis 2

Table 14.6-2.6 (page 1 of 1)
Objective Response Rate and Disease Control Rate
Population ITT

	Total
	N = xxxx
<hr/>	
Objective Response	
Patients with CR, n (%)	xx (xx.x%)
Patients with PR, n (%)	xx (xx.x%)
Objective Response Rate, n (%)	xx (xx.x%)
95% CI for Objective Response Rate	xx.x - xx.x
Disease Control	
Patients with CR, n (%)	xx (xx.x%)
Patients with PR, n (%)	xx (xx.x%)
Patients with SD, n (%)	xx (xx.x%)
Disease Control Rate, n (%)	xx (xx.x%)
95% CI for Disease Control Rate	xx.x - xx.x

[figure not shown]
Source: Listings 16.6-1.5

Table 14.6-2.7 (page 1 of 1)
Overall Survival Descriptive Statistics
Population ITT

	Total
	N = xxxx
25th Percentile (95% CI)	xx.xx (xx.xxx, xx.xxx)
Median (95% CI)	xx.xx (xx.xxx, xx.xxx)
75th Percentile (95% CI)	xx.xx (xx.xxx, xx.xxx)
Number Assessed	xx
Number Censored	xx
Number Uncensored	xx

Source: Listings 16.6-1.5

Figure 15.6-2.1 (page 1 of 1)
Kaplan Meier Plot for Progression Free Survival
Population ITT

Novartis
IMP : Everolimus
Protocol No.: CRAD001LIC01

Confidential

Date : 22SEP2017
Version : 2
Status : Final
Page : 64 of 101

Programming Note: Use same template for the following figures.

- Figure 15.6-2.2 Kaplan Meier Plot for Progression Free Survival - Sensitivity Analysis 1, Population ITT
- Figure 15.6-2.3 Kaplan Meier Plot for Progression Free Survival - Sensitivity Analysis 2, Population ITT
- Figure 15.6-2.4 Kaplan Meier Plot for Duration of Response, Population ITT
- Figure 15.6-2.5 Kaplan Meier Plot for Overall Survival, Population ITT

Novartis
 IMP : Everolimus
 Protocol No.: CRAD001LIC01

Confidential

Date : 22SEP2017
 Version : 2
 Status : Final
 Page : 65 of 101

Listing 16.1-1.1 (page 1 of n)
 End of Treatment Status

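### The only PFS-rate table shells split by cohort (SAP Tables 14.6-2.1 and 14.6-2.2) read Kaplan-Meier at data cut-off, so no table gives the PFS rate over time for first-line and second-line patients

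*SAP*

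**What the plan says.** Protocol 10.4.2 sets the primary analysis: "The primary analysis for this study is to estimate the PFS rate over time and its 95% CI by the method of Kaplan-Meier". It then lists three groups: all patients, first-line patients, and second-line patients (those with prior cytokine therapy).

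SAP 7.2.1 makes the rate specific. "The PFS rate is defined as the survival function at the end of the time point based on a Kaplan-Meier analysis", and "The time points at which PFS rate will be summarized are: 8 weeks, 20 weeks, 32 weeks, 44 weeks, 56 weeks", continuing every 12 weeks. SAP 7.6 commits to the output: "PFS rate and 95% confidence intervals will be presented graphically and tabulated, overall and by strata".

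The shells in SAP Section 11 do something else:

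- **Tables 14.6-2.1 and 14.6-2.2** (main and sensitivity analyses) have first-line, second-line and total columns, with a single rate row per analysis. The footnote to that row reads "PFS Rate = survival function at the time of data analysis cut-off based on a Kaplan-Meier analysis".
- **Table 14.6-2.3** has rows for weeks 8 to 56 and the note "Table continues for every 12 week assessment as appropriate until analysis data cut-off". It has no cohort columns, and its second page gives the median for the total only.
- **Table 14.6-2.4** repeats this layout for the sensitivity analyses. Its only instruction to repeat is "Programming Note: Repeat for Sensitivity Analysis 2".

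**The concern.** One SAP gives the primary quantity two definitions, and the shells with cohort columns carry the wrong one. Shells are what programmers build from and what quality control checks against, so the footnote may well prevail over the text.

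Data cut-off is a date. Patients enrolled over about 18 months have very different follow-up on that date, so no single time on the Kaplan-Meier axis corresponds to it. The natural result is the last value of each cohort's curve. Two cohorts with identical PFS could then show different rates only because one was enrolled later. The precision planned per cohort would not apply to either value.

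**Working it through.** **1. The plan's own precision figure.** SAP 3.5 and Protocol 10.7 size each cohort on a 95% CI for the 10-month PFS rate, centred at 0.50, using the normal approximation. Width = 2 × 1.96 × √(0.25/n).

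- n = 55: 0.264 (stated: about 0.27)
- n = 110: 0.187 (stated: about 0.19)

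Both reproduce. The design target is a rate at a fixed time, in each cohort.

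**2. Which tabulated week is that?** 10 months × (365.25/12)/7 = 43.5 weeks, and 44 weeks = 10.1 months. The week-44 row is therefore the rate the cohorts were sized for.

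**3. Where is it tabulated?**

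| Shell | Fixed weeks | Cohort columns |
|---|---|---|
| 14.6-2.1, 14.6-2.2 | No (cut-off only) | Yes |
| 14.6-2.3, 14.6-2.4 | Yes | No |

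The page counts leave no room for unstated cohort pages. Table 14.6-2.3 has 2 pages: the weeks, then the total summary. Table 14.6-2.4 has 4 pages, which is 2 sensitivity analyses × 2 pages. No table shell combines fixed weeks with cohorts.

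**4. How far apart are the two quantities?** This is a simulation for illustration, with 3000 cohorts per setting.

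Inputs from the documents:
- n = 55 per cohort.
- Scans at weeks 8, 20, 32 and so on, within ±1 week.
- 31 July 2009 to 30 January 2012 is 913 days, or 30.0 months. Less 18 months of enrolment, that leaves 12 to 30 months from first visit. Less screening of up to 35 days (1.15 months), follow-up from first dose is about 11 to 29 months.

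Assumptions not in the documents:
- Cut-off falls at the planned last visit.
- PFS is exponential, S(t) = 0.5^(t/median), with a median of 10 months to match the plan's 0.50.
- Dropout is 10% by 10 months, and 15% of events are deaths.

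Estimator: Kaplan-Meier, S(t) = Π(1 − dᵢ/nᵢ), with Greenwood SE = S·√Σ dᵢ/[nᵢ(nᵢ − dᵢ)] and width = 2 × 1.96 × SE. The rate at cut-off is taken as the curve at its last event.

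| Setting | Rate at cut-off | Rate at week 44 |
|---|---|---|
| Base case | 0.129 | 0.537 |
| Scans exactly on schedule | 0.160 | 0.496 |
| Follow-up 5–23 months | 0.179 | 0.517 |
| Follow-up 23–41 months | 0.068 | 0.537 |
| Follow-up 35–53 months | 0.036 | 0.538 |
| Cohort followed 20–29 months | 0.120 | 0.538 |
| Cohort followed 11–20 months | 0.202 | 0.536 |
| Median 3.8 months (Protocol 10.7) | 0.014 | 0.197 |
| Median 11.2 months (Protocol 10.7) | 0.154 | 0.573 |

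In the base case, the 5th to 95th percentile of the cut-off value is 0.00 to 0.29, with a median of 3 patients at risk. In 21.8% of cohorts the value is exactly 0, where a Greenwood term has nᵢ − dᵢ = 0 and there is no interval. The week-44 width is 0.271, in line with the plan. Dropout of 0% to 20% or a death share of 0% to 30% leaves the cut-off value at about 0.13 and week 44 at 0.53 to 0.54.

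A simpler simulation (scans on schedule, no dropout, follow-up 12 to 30 months, median 10 months) gives 0.152 at cut-off and 0.496 at week 44. The week-44 width is 0.262, with about 26 patients at risk.

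**The case against.** The strongest reply is that the method is correctly specified. SAP 7.2.1 fixes the weeks and SAP 7.6 commits to strata, so a programmer who reads the text will do the right thing. That is true, and it makes this a conflict between shell and text rather than a wrong method throughout. It does not remove the conflict.

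Several narrower points have some force:

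- Protocol 10.4.2 requires estimation by cohort and curves by strata, but only SAP 7.6 explicitly requires tabulation by stratum. The gap in tables is therefore chiefly a gap against the SAP.
- The Kaplan-Meier figure template is not visible in the text available and may plot strata. SAP 7.6 asks for both a graph and a table.
- The footnote may mean only that data are taken as of the cut-off date. The time point would then be unstated, which still does not yield the SAP 7.2.1 rate, and the simulated cut-off values would not be what the shell prescribes.
- The follow-up range rests on planned dates, and SAP Section 3 expects about 142 patients, not 110. If these split evenly (an assumption), 71 per cohort gives a binomial width of 0.233.
- The enrolment contrast of 0.12 against 0.20 assumes that the two cohorts were enrolled in separate halves of the period. With overlapping follow-up of 14–29 and 11–26 months, it shrinks to 0.126 against 0.151.
- With scans up to a week late, reading at nominal week 44 overstates the assumed true value of 0.5^(44/43.48) = 0.496. Reading at week 45 gives about 0.49. This follows from SAP 7.2.1 itself and affects the overall table equally; the fix does not add it.

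**Conclusion.** The point holds and should be fixed. As written, the shells give each cohort a rate at data cut-off that is not the rate defined in SAP 7.2.1. No table gives first-line and second-line PFS rates at the fixed weeks, including week 44, the row closest to the design's 10 months. This conclusion rests on the documents alone.

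The size is illustrative: about 0.13 against 0.54 per cohort under the base assumptions, with cut-off values from 0.01 to 0.20 across the settings tried. How large the gap is depends on follow-up and on the true PFS. A Kaplan-Meier curve cannot rise, so with follow-up beyond week 44 the cut-off value can never exceed the week-44 value. The overall rate by week is unaffected, because Table 14.6-2.3 provides it.

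**What to change.** - Present Tables 14.6-2.3 and 14.6-2.4 for first-line, second-line and total: the rate with 95% CI at every SAP 7.2.1 time point, and the median with 95% CI.
- In Tables 14.6-2.1 and 14.6-2.2, delete the cut-off rate and its footnote. Alternatively, replace it with the Kaplan-Meier rate and 95% CI at the SAP 7.2.1 time points, including week 44, read at the same times as in Table 14.6-2.3.
- While editing that footnote, correct its description of patients who progressed or died as having achieved PFS; they are the PFS events. This is wording only.

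The cost is column and footnote edits in four shells, and programming two tables by cohort. Stratum is already held per patient (Listing 16.1-1.2), so no new data are needed. SAP 7.2.1 and the protocol stay as they are.
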